## 15.5. PHYSICAL EXAMINATION

Physical examination assessments are as recorded on the Physical Examination eCRF.

Physical examination assessments will be listed for the Study population per body system by site/subject number, visits, date and time including any unscheduled assessments. Assessments post administration of anti-thyroid drugs will be flagged.

## 16. DATA NOT SUMMARIZED OR PRESENTED

In general all eCRF data will be presented.

The other variables and/or domains not summarized or presented are:

Subject initials.

Investigator electronic signature in the eCRF.

## APPENDIX 1. PROGRAMMING CONVENTIONS FOR OUTPUTS

### 1. DATES & TIMES

Depending on data available, dates and times will take the form DDMMYYYY HH:MM.

### 2. SPELLING FORMAT

English UK.

### 3. PRESENTATION OF VISITS

For outputs, visits will be represented as follows in the following order:

Long Name (default)
Screening
Baseline
Study Day 1
Week 2
Week 4
Week 6
Week 8
Week 12
Week 14
Week 16
Week 18
Week 22 (Follow-up)
Week 30 (Follow-up)
Early Termination
Unscheduled (chronologically)

Document: ATX\_GD\_59 Final 1.0 SAP 28FEB2018.docx  
Author: [name]

Version Number: Final 1.0  
Version Date: 28FEB2018

Template No: CS\_TP\_BS016 Revision 4  
Effective Date: 01Apr2016

Reference: CS\_WI\_BS005

Copyright © 2009, 2010, 2012, 2016 Quintiles Transnational Corp. All rights reserved.  
The contents of this document are confidential and proprietary to Quintiles Transnational Corp. Unauthorized use, disclosure or reproduction is strictly prohibited.

## 4. LISTINGS

All listings will be ordered by the following (unless otherwise indicated in the template):

- Site
- Subject Number
- Dose Level
- Visit
- Date/Time

---

Document: ATX\_GD\_59 Final 1.0 SAP 28FEB2018.docx  
Author: [name]

Version Number: Final 1.0  
Version Date: 28FEB2018

Template No: CS\_TP\_BS016 Revision 4  
Effective Date: 01Apr2016

Reference: CS\_WI\_BS005

Copyright © 2009, 2010, 2012, 2016 Quintiles Transnational Corp. All rights reserved.  
The contents of this document are confidential and proprietary to Quintiles Transnational Corp. Unauthorized use, disclosure or reproduction is strictly prohibited.

## APPENDIX 2. PARTIAL DATE/TIME CONVENTIONS

Imputed date/times will NOT be presented in the listings.

If Date/Time is available the following derivations will be applied:

- Pre-treatment AE (Screening period): Any AE that started or worsened in severity on or after informed consent and prior to the first administration of study drug.
- TEAE: Any AE that started or worsened in severity on or after the first administration of study drug up to and including 28 days after the last administration of study drug.
  - Titration dose level received prior to AE: Assign any AE that started or worsened in severity on or after that dose level received up to the date/time of the next dose level administration for each dose level, up to the first administration of full treatment period study drug (i.e., 2nd 800 µg dose).
  - Full treatment dose level received prior to AE: Assign any AE that started or worsened in severity on or after the first full treatment dose (i.e., 2nd 800µg dose) up to and including 28 days after the last administration of study drug.
- Non-TEAE commencing post-treatment: Any AE that started or worsened in severity more than 28 days after the last administration of study drug.

---

Document: ATX\_GD\_59 Final 1.0 SAP 28FEB2018.docx  
Author: [name]

Version Number: Final 1.0  
Version Date: 28FEB2018

Template No: CS\_TP\_BS016 Revision 4  
Effective Date: 01Apr2016

Reference: CS\_WI\_BS005

Copyright © 2009, 2010, 2012, 2016 Quintiles Transnational Corp. All rights reserved.  
The contents of this document are confidential and proprietary to Quintiles Transnational Corp. Unauthorized use, disclosure or reproduction is strictly prohibited.

## 1. ALGORITHM FOR TREATMENT EMERGENCE OF ADVERSE EVENTS:

Start Date/Time	Stop Date	Action
Partial, but known components show that it cannot be on or after first dose of study drug administration date/time	Known/Partial/Missing/Ongoing	Pre-treatment
*Partial, indicates to be on or after 25 µg start date but before next dose level		Assumed TEAE and 25 µg (titration period)
*Partial, indicates to be on or after 50 µg start date but before next dose level		Assumed TEAE and 50 µg (titration period)
*Partial, indicates to be on or after 100 µg start date but before next dose level		Assumed TEAE and 100 µg (titration period)
*Partial, indicates to be on or after 400 µg start date but before next dose level		Assumed TEAE and 400 µg (titration period)
*Partial, indicates to be on or after 1 st 800 µg start date but before next dose level		Assumed TEAE and 800 µg (titration period)
*Partial, indicates to be on or after 2 nd 800 µg start date but before 28 days after last administration of study drug		Assumed TEAE and 800 µg (full treatment period)
Partial, but known components show that it started more than 28 days after last administration of study drug date (section 7.7.4)		Non-TEAE
Partial, could be on or after study drug start date	Known	If AE end date < first study drug administration start date, then Pre-treatment If AE end date >= first study drug administration start date, then assume TEAE (Reference * for assignment of specific dose and treatment period)
	Partial	Impute end date as latest possible date (i.e. last day of month if day unknown or 31st December if day and

Document: ATX\_GD\_59 Final 1.0 SAP 28FEB2018.docx

Author: [name]

Version Number:

Final 1.0

Version Date:

28FEB2018

 Template No: CS\_TP\_BS016 Revision 4  
 Effective Date: 01Apr2016

Reference: CS\_WI\_BS005

Start Date/Time	Stop Date	Action
		month are unknown), then: If AE end date < first study drug administration start date, then Pre-treatment If AE end date >= first study drug administration start date, then assume TEAE (25 µg)
	Missing/Ongoing	Assumed TEAE and 25 µg
Missing	Known	If AE end date < first study drug administration start date, then Pre-treatment  If AE end date >= first drug administration start date, then assume TEAE (25 µg/titration period)
	Partial	Impute AE end date as latest possible date (i.e. last day of month if day unknown or 31st December if day and month are unknown), then:  If AE end date < first study drug administration start date, then Pre-treatment  If AE end date >= first study drug administration start date, then assume TEAE (25 µg)/titration period
	Missing /Ongoing	Assumed TEAE (25 µg)/titration period

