### **6.7.5. TREATMENT PERIOD**

Treatment period start for medications, procedures and AEs is defined as:

- First administration of study drug.

Titration period start for AEs, medications and procedures is defined as:

- First administration of study drug.

Full treatment period start for AEs, medications and procedures is defined as:

- First administration of full treatment period study drug (i.e., second dose of 800 µg).

Treatment period end for medications, procedures and AEs is defined as:

- Last administration of study drug date plus 28 days.
- For AEs onset dates/times are recorded, so the calculation of period starts/ends will take account of both dates and times.

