### **6.7.6. POST-TREATMENT PERIOD**

Post-treatment period start for medications, procedures and AEs is defined as:

- Last administration of study drug date plus 29 days. For AEs onset dates and times are recorded, so the calculation of period will take both onset dates and times into account.
- For AEs dates/times are recorded, so the calculation of period starts/ends will take account of both dates and times.

Any AE, medication or procedure with partially missing start date (and time for AEs) will be assigned on the basis of the information available and worst case principle. See Appendix 2: Partial Date Conventions for handling of partial dates for medications and procedures.

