### 15.1. ADVERSE EVENTS

Adverse events are recorded on the AEs eCRF and coded using MedDRA central coding dictionary, version 19.1.

An AE is defined as any untoward medical occurrence in a subject administered study drug that does not necessarily have a causal relationship with the treatment. An AE can therefore be any unfavourable and unintended sign (i.e., an abnormal laboratory finding), symptom (i.e., rash, pain, discomfort, fever, dizziness, etc.), disease (i.e., peritonitis, bacteraemia, etc.) or outcome of death temporally associated with the use of study drug, whether or not considered causally related to the study drug.

For the purpose of the analysis, AEs are allocated to the study periods based on the start date (and time where available) of the AE as follows:

- Pre-treatment AE (Screening period): Any AE that started or worsened in severity on or after informed consent and prior to the first administration of study drug.
- Treatment-emergent adverse events (TEAEs): Any AE that started or worsened in severity on or after the first administration of study drug up to and including 28 days after the last administration of study drug.
- Non-TEAE commencing post-treatment: Any AE that started or worsened in severity more than 28 days after the last administration of study drug.
- Study periods for AEs are mutually exclusive; therefore it can only be assigned to one period, namely pre-treatment, TEAE or Non-TEAE.

AEs will be further identified as being either titration period or full treatment period AEs according to the definitions below:

---

Document: ATX\_GD\_59 Final 1.0 SAP 28FEB2018.docx  
Author: [name]

Version Number: Final 1.0  
Version Date: 28FEB2018

Template No: CS\_TP\_BS016 Revision 4  
Effective Date: 01Apr2016

Reference: CS\_WI\_BS005

Copyright © 2009, 2010, 2012, 2016 Quintiles Transnational Corp. All rights reserved.  
The contents of this document are confidential and proprietary to Quintiles Transnational Corp. Unauthorized use, disclosure or reproduction is strictly prohibited.

- Titration period: Any AE that started or worsened in severity on or after the first administration of study drug up to the first full treatment period study drug (i.e., 2nd 800 µg dose) administration.

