- Full treatment period: Any AE that started or worsened in severity on or after the first administration of full treatment period study drug (i.e., 2nd 800 µg dose) administration up to and including 28 days after last administration of study drug.

TEAEs are mutually exclusive for assignment to either the titration or full treatment periods. Note that the first dose at 800 µg is in the titration period, and the full treatment period starts with the second dose of 800 µg.

Relationship, as indicated by the Investigator, is classed as 'not related', 'possibly related', 'probably related' or 'definitely related' (increasing severity of relationship). A drug-related AE is defined as an AE with a relationship to study drug of 'possibly related', 'probably related' or 'definitely related' or with a missing or unknown relationship to study drug. If a subject reports an AE more than once within that SOC and/or PT, the AE with the highest related assessment will be used in the corresponding summaries of relatedness.

Severity is classed as 'mild', 'moderate' or 'severe' (increasing severity). AEs with a missing severity will be classified as 'severe' (worst case). If a subject reports an AE more than once within that SOC and/or PT, the AE with the worst case severity will be used in the corresponding severity summaries.

See Appendix 2: Partial Date/Time Conventions for handling of partial dates/times for AEs. In cases where it is not possible to define an AE as treatment emergent or not, the AE will be classified by the worst case i.e. treatment emergent.

The following tables will be presented by dose level of study drug last received prior to onset of each individual subject's AE for the ITT population :

- An overview of the number and percentage (%) of subject and frequency of events will be provided for the following TEAEs per the dose levels per defined period (titration and full treatment periods) as well as overall:
  - TEAEs.
  - Drug related TEAEs.
  - Treatment-emergent serious adverse events (TESAEs).
  - Drug related TESAE.
  - TEAEs leading to death.
  - TEAEs leading to early study withdrawal.
  - TEAEs leading to dose interruption or suspension.

---

Document: ATX\_GD\_59 Final 1.0 SAP 28FEB2018.docx  
Author: [name]

Version Number: Final 1.0  
Version Date: 28FEB2018

Template No: CS\_TP\_BS016 Revision 4  
Effective Date: 01Apr2016

Reference: CS\_WI\_BS005

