**Note:**

Only scheduled visits adherence applicable to the study is to be validated according to the relevant visit window below. Visits not in accordance with the table below are to be identified by means of a flag on the listing of study visits:

---

Document: ATX\_GD\_59 Final 1.0 SAP 28FEB2018.docx  
Author: [name]

Version Number: Final 1.0  
Version Date: 28FEB2018

Template No: CS\_TP\_BS016 Revision 4  
Effective Date: 01Apr2016

Reference: CS\_WI\_BS005

Copyright © 2009, 2010, 2012, 2016 Quintiles Transnational Corp. All rights reserved.  
The contents of this document are confidential and proprietary to Quintiles Transnational Corp. Unauthorized use, disclosure or reproduction is strictly prohibited.

Visit	Protocol Study Day	Deviation if outside	Visit Window relative to date of first study drug administration
Screening visit (Week -4: )	Day -28 to -1	+ 5 days	Week -4: Day -33 to Day -1
Study day 1 visit	1	Not applicable	
Dose titration period visits	Week 2: Day 14 Week 4: Day 28 Week 6: Day 42 Week 8: Day 56	± 3 days	Week 2: Day 11 to 17 Week 4: Day 25 to 31 Week 6: Day 39 to 45 Week 8: Day 53 to 59
Full dose Treatment visits	Week 10: Day 70 Week 12: Day 84 Week 14: Day 98 Week 16: Day 112 Week 18: Day 126	± 3 days	Week 10: Day 67 to 73 Week 12: Day 81 to 87 Week 14: Day 95 to 101 Week 16: Day 109 to 115 Week 18: Day 123 to 129
Follow-up visits (Week 22)	Week 22: Day 154	± 3 days,	Week 22: Day 151 to 157
Follow-up visits (Week 30)	Week 30: Day 210	± 7 days	Week 30: Day 203 to 217

Study day is calculated relative to the date of first administration of study drug and is only presented for subjects with a study drug administration date (see section 6.1 ).

The ET visit will be allocated to a scheduled visit according to the table above, where the ET visit has occurred in place of the scheduled visit and is within the relevant visit window. Any ET visits will be reviewed for allocation to a scheduled visit, at the DR meeting.

Document: ATX\_GD\_59 Final 1.0 SAP 28FEB2018.docx  
Author: [name]

Version Number: Final 1.0  
Version Date: 28FEB2018

Template No: CS\_TP\_BS016 Revision 4  
Effective Date: 01Apr2016

Reference: CS\_WI\_BS005

Copyright © 2009, 2010, 2012, 2016 Quintiles Transnational Corp. All rights reserved.  
The contents of this document are confidential and proprietary to Quintiles Transnational Corp. Unauthorized use, disclosure or reproduction is strictly prohibited.

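### SAP Appendix 2 leaves an adverse event dated exactly 28 days after the last dose, with no clock time, outside both its full-treatment row and its non-TEAE row, although the rest of the SAP counts day 28 as on treatment

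*SAP*

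**What the plan says.** SAP section 15.1 allocates adverse events to periods "based on the start date (and time where available"), and counts an event as treatment-emergent (a TEAE) through day 28 after the last dose. Its full-treatment period runs from the second 800 µg "administration up to and including 28 days after last administration of study drug". Section 6.7.5 ends the treatment period at "Last administration of study drug date plus 28 days", and section 6.7.6 starts the post-treatment period at "Last administration of study drug date plus 29 days". The opening of Appendix 2, for events whose date and time are available, repeats the inclusive limit: "up to and including 28 days after the last administration of study drug".

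Section 15.1 refers events with partial dates or times to Appendix 2. In that table (Appendix 2, part 1) the starred full-treatment row ends differently: "but before 28 days after last administration of study drug". The non-TEAE row applies when "known components show that it started more than 28 days after last administration of study drug date". A further row takes partial starts that might fall on or after the first dose. Its outcome depends on the stop date:

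- **Known stop date, on or after the first dose:** TEAE, with the dose level referred back to the starred rows.
- **Partial stop date (imputed as late as possible), on or after the first dose:** TEAE under 25 µg.
- **Missing stop date or ongoing event:** TEAE under 25 µg.

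The visit table in Appendix 4, section 4.2 puts the last dosing visit (Week 18) at Day 126 and gives "Week 22: Day 154" for the first follow-up visit.

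**The concern.** Two adjacent rows of an operative programming rule leave a one-day hole between them. A programmer coding the table as written has no row for day 28, and the only other row that accepts partial starts leads to 25 µg in two of its three branches.

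Safety is the primary objective, and the TEAE tables are broken down by dose level. A day-28 event in a subject who completed dosing followed ten doses, the last six of them at 800 µg, so the lowest-dose column is plainly the wrong place for it. The boundary is also not an arbitrary day: section 3.1 itself describes Week 22 as 28 days after the last dose, so an event first noted at an on-schedule Week 22 visit and dated that day sits on it.

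**Working it through.** The check is a comparison of rules, not a power or sample-size calculation, and the plan states no figure to reproduce.

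**Boundary day.** Appendix 4, section 4.2 gives the Week 18 dose on Day 126 and the Week 22 visit on Day 154. 154 − 126 = 28.

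**Which events meet the gap.** The table's first column is start date and time together, and section 6.7.5 says that event periods take account of both. A complete date without a time can therefore be read as a partial start. This is the case that matters. When only the month is known, the known components cannot place the event on exactly day 28.

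**Applying each rule.** Let k be the number of days from the last dose to onset, for a subject dosed to Day 126, with the start date known and the time missing.

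- General rule (section 15.1 and the opening of Appendix 2): full-treatment TEAE if k ≤ 28, non-TEAE if k > 28.
- Appendix 2 table: full-treatment TEAE if k < 28, non-TEAE if k > 28, otherwise the catch-all row.

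| k | General rule | Table, stop date known | Table, stop date partial | Table, stop date missing or ongoing |
|---|---|---|---|---|
| 26 | 800 µg full treatment | 800 µg full treatment | 800 µg full treatment | 800 µg full treatment |
| 27 | 800 µg full treatment | 800 µg full treatment | 800 µg full treatment | 800 µg full treatment |
| 28 | 800 µg full treatment | TEAE, no dose level defined | TEAE, 25 µg | TEAE, 25 µg |
| 29 | non-TEAE | non-TEAE | non-TEAE | non-TEAE |

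The k = 28 row takes the catch-all literally. With a known stop date it points back to the starred rows, and none of them covers k = 28. Only day 28 differs from the general rule.

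**Is the exclusive limit deliberate?** Nothing suggests so. The companion algorithm for medications and procedures (Appendix 2, part 2) uses ≤ 28 days. Section 4.3.5 defines post-treatment events as those after 28 days, and section 4.3 announces no different limit for partial dates. The non-TEAE row's cross-reference does not settle it, because it cites section 7.7.4 and section 7 ends at 7.6.

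**With the fix.** Replacing k < 28 by k ≤ 28 sends day 28 to 800 µg full treatment for every stop-date status. Days 26, 27 and 29 do not change.

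**The case against.** The strongest reply is that the SAP already answers the question. Section 15.1 uses time only where it is available, which points to classifying a complete date without a time by date alone, and then day 28 is full treatment. No passage defines a missing clock time as a partial date. The catch-all row also tests whether the event ended before the first dose, which makes sense only when onset relative to the first dose is in doubt. That is never so 28 days after the last dose. On this reading nothing sends the event to 25 µg. The table is merely silent, and the dose-last-received rule in section 15.1 supplies 800 µg. Finally, Appendix 4, section 4.4 requires dose-level assignments for events with partial or missing dates or times to be confirmed at the data review.

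Most of this stands, and it limits the consequence. A reader might infer that the rule as written moves day-28 events from the highest to the lowest dose column. The documents do not establish that: it needs the literal reading of the catch-all row and a stop date that is partial, missing or ongoing. With a known stop date the dose level is undefined, not 25 µg.

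A reader might also take the visit windows as a measure of frequency. Of the 7 × 7 = 49 pairs of in-window days (123–129 and 151–157), 7 are exactly 28 days apart, or 14%. That describes visit spacing. It is not a rate of misassigned events, which would also need an onset dated that day, a missing time and the right stop-date status.

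What the reply does not remove is the contradiction. Section 15.1 itself refers partial dates and times to this table, and the table's limit disagrees with the section that refers to it. The data review would then be confirming assignments against two written rules that conflict.

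**Conclusion.** The row is wrong as written, with low impact. The full-treatment limit in the Appendix 2 table contradicts section 15.1, sections 6.7.5 and 6.7.6, and the opening of the same appendix. For an event dated exactly 28 days after the last dose with no clock time, it gives no valid dose level.

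The event remains a TEAE on every reading, since section 15.1 resolves doubt towards treatment-emergent. Overall TEAE counts are therefore unaffected. Only the dose-level and period columns can change, and section 15 plans no statistical comparison between dose levels.

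The size is one calendar day per subject. If a subject were wrongly counted in a column, that would be 1/12 ≈ 8% with the 12 subjects planned to complete, or 1/15 ≈ 7% with the approximately 15 planned to be dosed. The second is the nearer denominator for the 25 µg column, because every dosed subject starts there.

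The conclusion assumes that a missing clock time can bring an event into this table, which the column heading and section 6.7.5 allow but do not state outright. The documents do not say how often onset times will be missing, so no expected number of events can be given.

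**What to change.** In the starred full-treatment row of Appendix 2, part 1, replace "but before 28 days after last administration of study drug" with "up to and including 28 days after the last administration of study drug", keeping the second 800 µg dose as the start. Add one sentence making the table follow section 15.1: an adverse event with a complete start date and no time is classified by date at this boundary.

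The cost is one phrase, one sentence and the matching program line. No data collection or other output is affected. It should be done before the population and event assignments are confirmed at the data review, so that the meeting works from a single rule.

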Study periods for medications and procedures are mutually exclusive, therefore a medication or procedure can be only be assigned to one period, namely Prior, Concomitant or Post-treatment. Within concomitant medications and procedures the titration period and full treatment period are not mutually exclusive; hence a medication or procedure can be assigned to the titration period, full treatment period or both. Any medication ongoing during a treatment period will be included even if it started in an earlier period but has not ended before the start of the next period.

Note that the denominator for percentages of subjects is the total number of subjects in the ITT population with data available for the respective period. The denominator for percentages of events is the total number of events in the respective period.

See Appendix 2: Partial Date Conventions for handling of partial dates for medications/ procedures. In the case where it is not possible to define a medication/ procedure as prior, concomitant (titration period/full treatment period for medications), or post-treatment, the medication/ procedure will be classified by the worst case; i.e. titration period (concomitant) if it cannot be ruled out by the partial or missing date(s) recorded.

The following tables will be presented for the ITT population:

- The number (n) and percentage (%) of subjects with at least one medication and frequency of medications: Prior medication, concomitant medication taken during the treatment period, broken down by titration period and full treatment period, and overall and post-treatment medication taken more than 28 days after the last administration of study drug, will be presented overall and by Anatomic Therapeutic Class (ATC) Level 1 and within ATC Level 1 by ATC Level 3 and within ATC Level 3 and by WHO-DD Preferred Drug name. If medication occurred more than once for a subject within a period, the subject will only be counted once per ATC Level/Preferred drug name in that period.
- The number (n) and percentage (%) of subjects with at least one prior, concomitant (concomitant procedures occurring during the treatment period, broken down by titration period and full treatment period, and overall) and post-treatment procedures will be presented overall and by MedDRA SOC and within SOC by PT. If a procedure occurred more than once for a subject within a period, the subject will only be counted once per MedDRA SOC or PT in that period.

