	Missing/ongoing	
Impute medication/procedure start date as earliest possible date (i.e. first day of month if day unknown or 1st January if day and month are unknown), then :
 
If medication/procedure end date is missing could never be assumed a prior medication
 
Assign as titration period and full treatment period (Concomitant) unless, if medication/procedure start date >= first administration of full treatment period study drug (2nd 800 µg dose), assign as full treatment period (Concomitant)
 
If medication/procedure start date > 28 days after last administration of study drug date (section 7.7.4), assign as post-treatment

Missing	Known	
If medication/procedure end date < first study drug administration start date, assign as prior
 
If medication/procedure end date < full treatment period study drug (2nd 800 µg dose, assign as titration period (Concomitant)
 
Else assign as titration period and full treatment period (Concomitant).
 
Cannot be assigned as post-treatment

Start Date	End Date	Action
Missing	Partial	
Impute medication/procedure end date as latest possible date (i.e. last day of month if day unknown or 31st December if day and month are unknown), then:
 
If medication/procedure end date < first study drug administration start date, assign as prior
 
If medication/procedure end date < full treatment period study drug (2nd 800 µg dose, assign as titration period (Concomitant)
 
Else assign as titration period and full treatment period (Concomitant).
 
Cannot be assigned as post-treatment

	Missing/ongoing	Assign as titration period and full treatment period. (Concomitant)

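### Adverse events with a wholly missing start date default to 25 µg and titration, so the higher-dose and full-treatment columns of the by-dose tables can be understated

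*SAP*

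**What the plan says.** SAP 15.1 sets the layout of the safety tables: "The following tables will be presented by dose level of study drug last received prior to onset" of each subject's event. Appendix 2 applies the same principle to fully dated events in titration. An event goes to a dose level if it began "on or after that dose level received up to the date/time of the next dose level administration". Events from the second 800 µg dose until 28 days after the last dose form the full-treatment group. SAP 15.1 also states that "TEAEs are mutually exclusive for assignment to either the titration or full treatment periods".

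For a wholly missing start date, Appendix 2, section 1, has three branches:

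- **Stop date known.** Before first dose, the event is pre-treatment. Otherwise "If AE end date >= first drug administration start date, then assume TEAE", at 25 µg in titration.
- **Stop date partial.** It is imputed to the latest possible date, and then "If AE end date >= first study drug administration start date, then assume TEAE", again at 25 µg in titration.
- **Stop date missing or event ongoing.** TEAE at 25 µg in titration.

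On events that cannot be classified, SAP 15.1 says that "the AE will be classified by the worst case i.e. treatment emergent". This settles treatment emergence and names no dose level.

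**The concern.** Safety and tolerability is the primary objective, and in this within-subject escalation the by-dose TEAE tables show how tolerability changes as the dose rises. Treating an undated event as treatment-emergent is conservative. Placing it at the lowest dose is not conservative for a by-dose display, because any error about an on-treatment event runs one way. No level lies below 25 µg, so a misplaced event always moves down. A TEAE counts in one period only, so an event given to titration is also lost from full treatment.

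The stop date is used only to test whether the event ended before first dose. Beyond that, the rule does not ask which dose levels the stop date leaves possible.

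**Working it through.** The plan states no figure for this rule, so there is none to reproduce. The check lists the outcomes of the rule and then compares them with the dosing calendar.

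**Outcomes of the rule.** Three of three branches that do not end before first dose lead to 25 µg and titration. None leads to 50, 100, 400 or 800 µg, or to full treatment.

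**Is there another dose rule?**
- SAP 6.7.6 calls for the available information and a worst-case principle, but only for partially missing starts.
- SAP 15.1 uses worst case to mean treatment-emergent.
- SAP Appendix 4, section 4.4, has the data review meeting confirm these assignments but gives no rule for changing them.

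**Inputs for size**
- Dosing every 14 ± 3 days (Protocol synopsis; SAP 4.1).
- Ten doses, with full treatment starting at the second 800 µg dose, Week 10 (SAP 6.7.5; SAP 4.2).
- TEAE window ending 28 days after the last dose (SAP 6.7.5).
- About 15 treated and 12 evaluable subjects (Protocol synopsis).
- Assumptions, not in the documents: onset uniform over the window, and no help from the stop date.

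**Ten doses at nominal intervals**
- Window: 9 × 14 + 28 = 154 days.
- At 25 µg: 14/154 = 9.1%. Above 25 µg: 140/154 = 90.9%.
- In full treatment: (154 − 70)/154 = 84/154 = 54.5%.

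**Range over the dosing window**
- All intervals 11 days: window 9 × 11 + 28 = 127. Above 25 µg: 1 − 11/127 = 91.3%. Full treatment: (127 − 55)/127 = 56.7%.
- All intervals 17 days: window 9 × 17 + 28 = 181. Above 25 µg: 1 − 17/181 = 90.6%. Full treatment: (181 − 85)/181 = 53.0%.

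**Fewer doses.** With k doses the window is 14(k − 1) + 28, and the share placed too low is as follows.

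| Doses received | Window (days) | Share placed too low |
|---|---|---|
| 1 | 28 | 0% (only 25 µg was given) |
| 2 | 42 | 1 − 14/42 = 66.7% |
| 5 | 84 | 1 − 14/84 = 83.3% |
| 10 | 154 | 1 − 14/154 = 90.9% |

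**When the stop date is known.** The share of possible on-treatment onset days that lie at 25 µg is 14/20 = 70% for a stop at day 20 after first dose, 14/70 = 20% at day 70, and 14/100 = 14% at day 100. In the last case 30/100 = 30% of those days lie in full treatment. The rule gives the same answer each time.

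**One subject.** If the subject has no other counted event in that column, one misplaced event changes incidence by 1/15 = 6.7 points, or 1/12 = 8.3 points if 12 subjects are in the denominator.

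**The case against.** The strongest reply is that the rule may never be used. Onset dates and times are recorded for AEs (SAP 6.7.5), AEs are recorded at every visit (SAP 4.2), and data management must resolve queries before the data review (Appendix 4, section 2). With about 15 treated subjects, the number of wholly missing starts may be zero. This stands, and it limits the size of the point.

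There are also safeguards. The data review meeting discusses unresolved issues that could affect the analysis or require SAP revision (Appendix 4, sections 1 and 4.4). Imputed dates are not shown in listings, so a reader can see that a start is missing. No tests compare dose levels (SAP 15), and a subject counts once per term, so a misplaced event need not change incidence. All of this stands. What is missing is a reassignment rule fixed before the affected cases are discussed.

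Finally, the default is explicit and reproducible, and SAP 12 also sends unclassifiable medications to titration. A reader might infer from the medication algorithm that the SAP contradicts itself, because that algorithm counts a record with start and stop both missing in both periods. The documents do not support this: "Within concomitant medications and procedures the titration period and full treatment period are not mutually exclusive", whereas for TEAEs they are. The contrast shows only that an undated medication stays visible in full treatment and an undated AE does not.

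**Conclusion.** The point holds and is minor. Applied as written, the rule places undated on-treatment events at the lowest dose whatever their stop date, and any resulting error lowers the higher-dose and full-treatment columns. The figures of about 91% and 55% are upper-end illustrations that depend on ten doses, uniform onset and an uninformative stop date. They are shares of a count that the documents do not give. Overall TEAE counts do not change.

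Three stronger readings are tempting and are not supported:

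- **That the default is wrong unless the stop date precedes the 50 µg dose or only one dose was given.** With treatment emergence assumed, those are the only cases in which the dates establish 25 µg. An event that began at 25 µg and lasted longer is also placed correctly, though by chance.
- **That the tables will be materially distorted.** Nothing in the documents shows that any such event exists.
- **That Appendix 2 plainly sends month-only starts to 25 µg even when the month excludes it.** The residual row for partial starts can be read as covering only dates that straddle first dose, and SAP 6.7.6 tells the analyst to use the available information. What can be said is that a month spanning several dose levels matches none of the level-specific rows and needs clarification.

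**What to change.** In Appendix 2, section 1:

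- Keep the assumption of treatment emergence.
- Assign a dose level and period only where the known start and stop components leave a single one.
- Put all other such events in a footnoted 'dose not determinable' column that counts in the overall column, with all treated (ITT) subjects as its incidence denominator.
- Where the level cannot be determined but the period can, keep the event in that period. An example is a stop date after the 50 µg dose but before the second 800 µg dose, which leaves only titration.
- Apply the same rule to month-only starts that span several levels, consistent with SAP 6.7.6.

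In SAP 15.1, amend the two-way period assignment to allow a 'period not determinable' category, and add the denominator above to the existing dose-level and period denominators. In Appendix 4, section 4.4, state that the data review meeting applies this rule.

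The cost is small edits to these sections, one extra column in the by-dose TEAE tables and minor programming. The drawback is a column that may be empty.
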